3 TREATMENT INFORMATION

3.1 Surgery

3.1.1 Salvage Oligometastasectomy

All subjects with pelvic and/or para-aortic lymph node metastases will undergo surgical dissection covering the bilateral nodal group identified by molecular imaging (e.g., fluciclovine PET/CT or PSMA PET/CT scan or other per PI discretion), and one level above and one level below any identified nodal region.

Nodal groups from distal to proximal include: 1) Obturator fossa, 2) External iliac, 3) Common iliac, 4) Aortic-below IMA, 5) Aortic-above IMA.

Metastases to superficial inguinal nodes will also be considered for surgical dissection in which cases both a superficial inguinal lymph node dissection and pelvic lymph node (obturator fossa and external iliac nodes) dissection will be performed.

3.1.2 Salvage Prostatectomy

Subjects previously treated with definitive radiotherapy whose TRUS biopsy is positive for malignancy when screening for the study (see inclusion criterion 5.1.4) must undergo salvage prostatectomy (or salvage radiotherapy if applicable, see Section 3.2.1). This can be done prior to enrollment on the study or at the same time as the nodal dissection described in Section 3.1.1 above.

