Statistical Methodology	The planned sample size is N = 20 evaluable subjects. The primary outcome variable of reduction in PSA $\geq 50\%$ at 6 months will be analyzed descriptively via 90% and 95% exact binomial confidence intervals. No hypothesis test will be performed on the primary outcome variables. The sample size is justified by the width of the 95%

	confidence intervals. We anticipate that the PSA 50% response rate at 6 months will be 30% based on the results published by Siriwardana, as their PSA response at 6 weeks and 12 months was 43% and 23% respectively. However, the definition used here is somewhat different than the definition in that clinical study. If the observed PSA 50% response rate is 30% (6/20), the 95% exact binomial confidence interval (Clopper-Pearson) will be 12% to 54 %. With 20 evaluable subjects the maximum width of a 95% exact binomial confidence interval is 46% (27% to 73%) and occurs when the observed response rate is 50% (10/20).
--	---

SCHEMA

Figure 1: Overall Treatment Schema (All Arms)

[figure not shown]
[figure not shown]

Figure 2: Adjuvant radiotherapy (Arms B and C only)

1. With completion of prostate radiotherapy (for patients who received an incomplete definitive radiation course) OR salvage prostatectomy if positive baseline TRUS biopsy (including subjects enrolled in Arm A)
2. Bone radiotherapy can be completed prior to surgical resection if indicated in the opinion of the investigator.
3. Ipsilateral involved-field radiotherapy to 45 Gy in 25 fractions using image-guided IMRT
4. Simultaneous integrated boost to gross target volumes to be ≥ 76 Gy EQD2
5. Target volume defined with inferior dosimetric border set immediately above the previously treated area. Nodal volumes will be treated to 50.4 Gy. The prostate fossa will be treated for post-prostatectomy patients who have not had any radiation to the prostate fossa.

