5.1 Inclusion Criteria

Yes/No (Response of "no" = subject ineligible)

5.1.1 _____ Male subjects age \geq 18 years.

5.1.2 _____ Histologically proven adenocarcinoma of the prostate.

5.1.3 _____ Recurrent prostate carcinoma after definitive therapy for primary disease defined as:

- Post-prostatectomy (with/without adjuvant radiotherapy): Patients must have a detectable or rising PSA level that is >0.05 ng/mL, with a second confirmatory level that is >0.05 ng/mL after a minimum of 1 week.
- Post radiotherapy/ablation (without radical prostatectomy): PSA rise ≥ 2 ng/mL over nadir.

5.1.4 _____ Subjects treated with prior definitive radiotherapy for prostate cancer who have positive molecular imaging (e.g., fluciclovine PET/CT or PSMA PET/CT scan or other per PI discretion) suggesting recurrent intraprostatic disease must undergo TRUS biopsy less than or equal to one year before study enrollment:

- If the TRUS biopsy is negative, no additional treatment is required to the prostate in addition to that of scan-positive sites.
- If the TRUS biopsy is positive, subject must undergo salvage prostatectomy or salvage radiotherapy to the primary site concurrently with the study treatment per the treatment protocol algorithm.
- Note: Biopsy is not required for prostate fossa recurrences after radical prostatectomy.

5.1.5 Oligometastatic disease defined as 10 or fewer metastatic lesions to lymph nodes and/or bones only.

5.1.6 For patients with oligometastatic disease involving lymph nodes, metastasis is confined to the pelvic or para-aortic (below IMA) regions on molecular imaging (e.g., fluciclovine PET/CT or PSMA PET/CT scan or other per PI discretion).

5.1.7 All subjects must be surgical candidates if surgery is indicated per the treatment algorithm.

5.1.8 ECOG Performance Status ≤ 2 .

5.1.9 Use of condoms for male subjects who have not had surgical removal of their prostate and have a partner of child bearing potential beginning at the time of ICF signature and lasting until at least 6 months after the last radiation treatment. Because of the potential side effect on spermatogenesis associated with radiation, female partners of childbearing potential must agree to use a highly effective contraceptive method during and for 6 months after completing treatment.

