5.2 Exclusion Criteria

Yes/No (Response of “yes” = subject ineligible)

5.2.1 Known brain or visceral metastases other than lymph nodes (defined in section 5.1.6) as defined by CT, MRI, or other molecular imaging (e.g., fluciclovine PET/CT or PSMA PET/CT scan or other per PI discretion).

5.2.2 Patients actively receiving hormone therapy for prostate cancer. Patients may have received hormone therapy previously but must have documented non-castrate levels of testosterone (>50 ng/dL).

5.2.3 Prior or concurrent malignancy whose natural history or treatment, in the opinion of the enrolling investigator, may have the potential to interfere with the safety or efficacy assessment of the investigational treatment protocol of this study.

5.2.4 _____ Use of finasteride within 30 days prior to initiation of therapy. Baseline PSA should not be obtained prior to 30 days after stopping finasteride.

5.2.5 _____ Use of dutasteride within 90 days prior to initiation of therapy. Baseline PSA should not be obtained prior to 90 days after stopping dutasteride.

5.2.6 _____ Use of any prohibited therapy noted in 6.3.2.

5.2.7 _____ Active, uncontrolled, significant intercurrent or recent illness including, but not limited to, the following conditions:

- Cardiovascular disorders:
 - Congestive heart failure New York Heart Association Class 3 or 4, unstable angina pectoris, serious cardiac arrhythmias.
 - Uncontrolled hypertension defined as sustained blood pressure (BP) > 150 mm Hg systolic or > 100 mm Hg diastolic despite optimal antihypertensive treatment.
 - Stroke (including transient ischemic attack [TIA]), myocardial infarction (MI), or other ischemic event, or thromboembolic event (e.g., deep venous thrombosis, pulmonary embolism) within 6 months before first dose.
- Acute bacterial or fungal infection requiring intravenous antibiotics at the time of registration
- Chronic obstructive pulmonary disease exacerbation or other respiratory illness requiring hospitalization or precluding study therapy at the time of registration or within 30 days of registration.
- Hepatic insufficiency resulting in clinical jaundice and/or coagulation defects;

I certify that this subject meets all inclusion and exclusion criteria for enrollment onto this study.

Investigator Signature

Date

Time

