6.2.1 Oligometastasectomy

Subjects with pelvic or para-aortic lymph node metastases will undergo surgical dissection. Treatment will cover the bilateral nodal group identified by molecular imaging (e.g., fluciclovine PET/CT or PSMA PET/CT scan or other per PI discretion), and one level above and one level below any identified nodal region.

Nodal groups from distal to proximal include: 1) Obturator fossa, 2) External iliac, 3) Common iliac, 4) Aortic-below IMA, 5) Aortic-above IMA.

Metastases to superficial inguinal nodes will also be considered for surgical dissection in which cases both a superficial inguinal lymph node dissection and pelvic lymph node (obturator fossa and external iliac nodes) dissection will be performed.

For subjects who were treated with definitive radiotherapy pre-study and have a positive TRUS biopsy at baseline, or less than or equal to a year before study enrollment, salvage prostatectomy will be performed along with the procedure described above (unless salvage radiotherapy is indicated as described in Section 3.2.1).

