6.3.2 Prohibited Therapy

- Concurrent anti-cancer therapy (chemotherapy, androgen deprivation therapy, immunotherapy, biologic therapy, or tumor embolization) and external beam radiation other than those specified in this protocol.
- Concurrent use of another investigational drug or device therapy (i.e., outside of study treatment) during, or within 4 weeks of trial entry (signing of the informed consent form).
- Major surgery within 30 days prior to enrollment.

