8 STUDY CALENDAR

8.1 Arm A

Procedures	Screening ¹ (-4 weeks)	On Treatment		Follow-up ²	
		Salvage Therapy	Response Assessment ³ (45 days ± 5 days after last day of RT)	Year 1 (Q3M ± 2 weeks)	Year 2-3 (Q3M ± 1 month)
		Radiation			
Informed Consent	X				
Medical History ⁴	X				
Eligibility Criteria	X				
Clinical Assessments					
Vital Signs, Weight ⁵	X		X	X	X
Physical Exam	X		X	X	X
ECOG Performance Status	X		X	X	X
Adverse Event Collection ⁶		At each visit			
Concomitant Medication Collection	X	At each visit			
Laboratory Studies					
Hematology ⁷	X				
Chemistry ⁸	X				
LDH	X				
PSA ⁹	X		X	X	X
Disease Assessments					
Molecular imaging (e.g., fluciclovine PET/CT or PSMA PET/CT scan or other per PI discretion) ¹⁰	X				
CT Scans				X ¹¹	X ¹¹
Nuclear Medicine Bone Scans (if clinically indicated)	X			X ¹²	X ¹²
TRUS Biopsy ¹³	X				
Intervention					
SBRT or Hypofractionated Bone Radiotherapy		X			
Correlative Studies					
Optional Blood ¹⁴	X	X	X ¹⁵		
Optional Archival Tissue ¹⁶	X				
Optional Fresh Tissue ¹⁷	X				
Questionnaires					
PRO and QOL Questionnaires ¹⁸	X		X	X	X
RTOG Toxicity Evaluation ¹⁹			X	X	X

¹ All pre-study/screening procedures should be completed within 4 weeks of study enrollment - with the exception of laboratory tests which need to be completed within 2 weeks prior to study enrollment, and imaging assessments which must be completed within 90 days of enrollment.

² Follow-up procedures will occur every 3 months for 3 years beginning from the last day of RT unless stated otherwise.

³ The response assessment visit will take place 45 ± 5 days after completion of salvage therapy (surgery and/or radiation).

⁴ To include Charlson Comorbidity Index (See Appendix E)

⁵ Vital signs include systolic/diastolic blood pressure, heart rate, respiration rate, pulse oximetry, and body temperature. Height will be captured at screening only.

⁶ Adverse events will be assessed after treatment has begun and at each time a patient is seen in clinic or scheduled for correlative sample collections. Adverse events will be collected every three months for one year after treatment discontinuation.

⁷ Hematology includes CBC with differential and platelets.

⁸ Chemistry includes sodium, potassium, chloride, carbon dioxide or bicarbonate, blood urea nitrogen (BUN), creatinine, glucose, total protein, albumin, calcium, AST, ALT, alkaline phosphatase, total bilirubin.

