9.2.1 Salvage Therapy

- Oligometastasectomy for subjects with nodal metastases (Arms B or C, without or with bone metastases).
 - Subjects who have received a full course of definitive prostate radiotherapy and whose TRUS biopsy is positive at screening (or less than or equal to one year before enrollment) can undergo simultaneous salvage prostatectomy, or, if their initial dose of radiation was felt to be insufficient, complete a course of salvage prostate radiotherapy.
 - Some optional tissue resected during the procedures (oligometastasectomy and/or prostatectomy) may be collected for correlative research purposes if available after SOC tissue collection.
- SBRT (or hypofractionated RT) for subjects with bone metastases only (Arm A).
- For subjects with both nodal and bone metastases, surgery will take place on Day 1 and SBRT will follow once the subject has recovered from surgery. (Arm C)

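### Salvage prostatectomy may fall before or after the screening PSA, and the planned tables cannot separate the PSA fall from treating the prostate from response of the metastases

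*Combined protocol and SAP*

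**What the plan says.** The subjects concerned had earlier definitive radiotherapy and have a positive TRUS biopsy. The protocol gives the timing of their salvage prostatectomy in four places:

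- Section 3.1.2: "This can be done prior to enrollment on the study or at the same time as the nodal dissection".
- Inclusion criterion 5.1.4, for a positive biopsy: "subject must undergo salvage prostatectomy or salvage radiotherapy to the primary site concurrently with the study treatment".
- Section 6.2.1: "salvage prostatectomy will be performed along with the procedure described above", unless salvage radiotherapy is indicated.
- Section 9.2.1 is permissive: these subjects "can undergo simultaneous salvage prostatectomy" or, if the initial dose was judged insufficient, complete a course of prostate radiotherapy.

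Two windows fix where the screening PSA falls. Section 6.3.2, applied through exclusion 5.2.6, prohibits "Major surgery within 30 days prior to enrollment". The calendars in 8.1 to 8.3 refer to "laboratory tests which need to be completed within 2 weeks prior to study enrollment", and PSA is one of those tests.

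Sections 1.1, 10.1 and 11.3 define the primary response as a PSA fall of at least 50% at 6 months after all salvage and adjuvant treatment, without naming the starting value. Section 5.2.4 mentions one in passing ("Baseline PSA should not be obtained prior to 30 days after stopping finasteride") but does not define it. Section 11.3 reports the proportion with an exact 95% interval for all evaluable subjects and by arm. No split by treatment to the prostate is planned.

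**The concern.** The primary objective is response to treatment of oligometastatic disease, and section 2 intends the result as a reference for later trials. No hypothesis is tested, so the descriptive rate is the trial's main product and its meaning matters more than usual.

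Two similar men could be scored differently because of surgical scheduling. If the prostate is removed before enrolment, its PSA is outside the screening value and the fall measured on study comes from the remaining disease. If it is removed with the nodal dissection, its PSA is in the screening value and its removal contributes to the fall. Biopsy-positive subjects who instead complete prostate radiotherapy on study (section 3.2.1) raise the same attribution problem. One pooled proportion combines these cases, and the split by arm does not separate them.

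**Working it through.** **The plan's own figures.** Clopper-Pearson 95% limits reproduce section 11.1: 6/20 gives 11.9% to 54.3% (plan: 12% to 54%); 10/20 gives 27.2% to 72.8%, width 45.6 points (plan: 46). Those figures are not in dispute.

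**Position of the screening PSA.** Surgery before enrolment must be at least 30 days before it (6.3.2). The screening PSA is at most 14 days before it (calendars). The smallest gap is 30 − 14 = 16 days, so the draw always follows a pre-enrolment prostatectomy. A concurrent prostatectomy is study treatment given after enrolment, so the draw always precedes it. The calendars schedule no other PSA before treatment.

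**Effect on one subject.** Assumptions, not in the documents: a share p of the PSA comes from the prostate; prostatectomy removes all of that share, and in the pre-enrolment case it has cleared by the screening draw; the rest is unchanged until nodal or bone treatment lowers it by a fraction m.

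- Pre-enrolment: fall = m, so response needs m ≥ 50%.
- Concurrent: fall = 1 − (1 − p)(1 − m), so response needs m ≥ 1 − 0.5/(1 − p).

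| p | m needed, concurrent | m needed, pre-enrolment |
|---|---|---|
| 10% | 44.4% | 50% |
| 20% | 37.5% | 50% |
| 30% | 28.6% | 50% |
| 40% | 16.7% | 50% |
| 50% | 0% | 50% |

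Example with p = 20%, m = 40% and PSA 4.0 ng/mL before any surgery. The non-prostate part is 4.0 × 0.8 = 3.2, and after treatment 3.2 × 0.6 = 1.92. Concurrent: 1 − 1.92/4.0 = 52%, a responder. Pre-enrolment: 1 − 1.92/3.2 = 40%, a non-responder.

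**Effect of timing on the pooled rate.** One reclassified subject moves it by 1/20 = 5 points. For expected values, assume k of 20 subjects have salvage prostatectomy. Response is 30% (the plan's anticipated rate) except in concurrent prostatectomy subjects, where it is q, between 60% and 100%. If all k are operated on before enrolment, the expected rate is 30%. If all are concurrent, it is (0.30 × (20 − k) + q × k)/20:

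- k = 2: (5.4 + 1.2)/20 = 33% to (5.4 + 2.0)/20 = 37%.
- k = 4: (4.8 + 2.4)/20 = 36% to (4.8 + 4.0)/20 = 44%.

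**What an extra row would show.** Suppose six other subjects respond and every subject treated to the prostate on study responds only through the prostate. With one such subject, the pooled result is 7/20 = 35% (15.4% to 59.2%) and the restricted row 6/19 = 32% (12.6% to 56.6%). With two, it is 8/20 = 40% (19.1% to 63.9%) against 6/18 = 33% (13.3% to 59.0%). This illustrates the row; it does not measure the timing effect.

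**Precision of the extra row.** Maximum 95% width is 45.6 points at n = 20, then 46.7, 48.0, 49.2 and 50.7 at n = 19, 18, 17 and 16.

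**The case against.** The strongest reply is that this is the ordinary line between prior and study therapy. The study summary lists prostatectomy as study treatment and the endpoint is taken after all treatment, so counting its effect is what the plan says. A man operated on before enrolment must qualify under the post-prostatectomy criterion in 5.1.3, like every other post-prostatectomy recurrence, and none of those subjects is credited with the removal of the prostate. This stands. A reader might infer that the pooled rate is wrong or that concurrent prostatectomy should be removed from it; the documents support neither.

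A reader might also infer that the endpoint has no usable starting value. That goes too far: section 10.1 invokes PCWG3, Appendix F speaks of change from baseline, and only one pre-treatment PSA is scheduled. Naming it is missing detail.

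Nor is Arm A left without a timetable. A schema note provides for "OR salvage prostatectomy if positive baseline TRUS biopsy (including subjects enrolled in Arm A"), and calendar 8.1 has no prostatectomy row. But footnote 3 of that calendar already counts the response visit from completion of salvage surgery and/or radiation, and section 9.3 counts follow-up from completion of all study treatment. The missing row is clerical and forms no part of this point.

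Finally, the study is descriptive and the affected group may be empty. That limits the importance of the point but does not remove the conflict in timing or the gap in the tables.

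**Conclusion.** The point holds as a cheap improvement. Section 3.1.2 conflicts with 5.1.4 and 6.2.1 on timing. Following 3.1.2 gives a 50% fall two meanings within one proportion, and no planned analysis separates treatment of the prostate, by surgery or completion radiotherapy, from response of the metastases.

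The size is unknown. The documents do not say how many subjects will have salvage treatment to the prostate. Each reclassified subject is worth 5 points; on the assumptions above, timing moves the expected rate 3 to 7 points with two prostatectomy subjects and 6 to 14 with four. The values of p, m and q are assumptions, and the per-subject model describes prostatectomy only. The illustrative intervals overlap heavily, so the issue is what the rate means, not how precisely it is estimated. The sample-size justification is unaffected.

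**What to change.** 1. Make 3.1.2 agree with 5.1.4 and 6.2.1: a salvage prostatectomy required by the protocol is done on study, after the screening PSA. A subject operated on before enrolment who qualifies under the post-prostatectomy criterion in 5.1.3 is handled as having had prior therapy, with the screening PSA as reference.
2. Keep the primary proportion for all evaluable subjects. Add one row, with its exact 95% interval, excluding subjects who had any salvage treatment to the prostate on study (prostatectomy or completion prostate radiotherapy), measured from the screening PSA.

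Leave the pre-resection reference in 6.2.3.2 as it is; it serves the adjuvant decision. The Arm A calendar row can be added as a clerical correction at the same time.

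The cost is an amendment and one table row, with no extra visits or samples. The added row is less precise: its maximum width is about 47 to 51 points if 1 to 4 subjects are excluded, against 46 for all 20. It also does not isolate the metastases completely, since adjuvant radiotherapy to the prostate fossa (schema note 5) remains in it. The pre-enrolment route in 3.1.2 would close; how many candidates would have used it is not stated.

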3.2 External Beam Radiation Therapy

Radiation therapy will be performed on linear accelerators capable of delivering X-ray or electron therapy in the 4 to 18 MeV range with image guidance systems. One of the fractionation schemes listed in Section 6 will be used.

3.2.1 Salvage Radiotherapy for Subjects with Positive TRUS Biopsy at Baseline

Subjects previously treated with an incomplete course of definitive radiotherapy (as defined according to institutional standards) who have positive molecular imaging (e.g., fluciclovine PET/CT or PSMA PET/CT scan or other per PI discretion) suggesting recurrent intraprostatic disease and whose TRUS biopsy is positive for malignancy when screening for the study (see inclusion criterion 5.1.4) must undergo completion of their radiation course or salvage prostatectomy as defined in section 3.1.2.

4 STUDY DESIGN

4.1 Description

This is a Phase II non-randomized pilot study meant to establish preliminary reference response rate and duration of response for subjects with recurrent prostate cancer treated with salvage oligometastasectomy and/or radiotherapy. Treatment decisions will be based on molecular imaging (e.g., fluciclovine PET/CT or PSMA PET/CT scan or other per PI discretion): subjects with nodal disease only will be treated with oligometastasectomy, subjects with bone disease only will be treated with SBRT, and subjects with a combination of nodal and bone disease will receive both treatment. Response rates and durations will be based on PSA and imaging.

4.2 Number of Subjects

A total of twenty (20) subjects will be enrolled on this study.

4.3 Number of Study Centers

This study will open at a single center at the Huntsman Cancer Institute.

4.4 Study Duration

The estimated duration of accrual is 2 years, subjects will be followed for up to 3 years for a total study duration of up to 5 years.

5 ELIGIBILITY CRITERIA

This eligibility checklist is used to determine subject eligibility and filed with the enrolling investigator's signature in the subject research chart.

Subject No. _____

Subject's Initials: (L,F,M) _____

5.1 Inclusion Criteria

Yes/No (Response of "no" = subject ineligible)

5.1.1 _____ Male subjects age \geq 18 years.

5.1.2 _____ Histologically proven adenocarcinoma of the prostate.

5.1.3 _____ Recurrent prostate carcinoma after definitive therapy for primary disease defined as:

- Post-prostatectomy (with/without adjuvant radiotherapy): Patients must have a detectable or rising PSA level that is >0.05 ng/mL, with a second confirmatory level that is >0.05 ng/mL after a minimum of 1 week.
- Post radiotherapy/ablation (without radical prostatectomy): PSA rise ≥ 2 ng/mL over nadir.

5.1.4 _____ Subjects treated with prior definitive radiotherapy for prostate cancer who have positive molecular imaging (e.g., fluciclovine PET/CT or PSMA PET/CT scan or other per PI discretion) suggesting recurrent intraprostatic disease must undergo TRUS biopsy less than or equal to one year before study enrollment:

- If the TRUS biopsy is negative, no additional treatment is required to the prostate in addition to that of scan-positive sites.
- If the TRUS biopsy is positive, subject must undergo salvage prostatectomy or salvage radiotherapy to the primary site concurrently with the study treatment per the treatment protocol algorithm.
- Note: Biopsy is not required for prostate fossa recurrences after radical prostatectomy.

5.1.5 Oligometastatic disease defined as 10 or fewer metastatic lesions to lymph nodes and/or bones only.

5.1.6 For patients with oligometastatic disease involving lymph nodes, metastasis is confined to the pelvic or para-aortic (below IMA) regions on molecular imaging (e.g., fluciclovine PET/CT or PSMA PET/CT scan or other per PI discretion).

5.1.7 All subjects must be surgical candidates if surgery is indicated per the treatment algorithm.

5.1.8 ECOG Performance Status ≤ 2 .

5.1.9 Use of condoms for male subjects who have not had surgical removal of their prostate and have a partner of child bearing potential beginning at the time of ICF signature and lasting until at least 6 months after the last radiation treatment. Because of the potential side effect on spermatogenesis associated with radiation, female partners of childbearing potential must agree to use a highly effective contraceptive method during and for 6 months after completing treatment.

5.1.10 Recovery to baseline or \leq Grade 1 CTCAE v5 from toxicities related to any prior treatments, unless AE(s) are clinically non-significant and/or stable on supportive therapy as determined by the treating physician.

5.1.11 Able to provide informed consent and willing to sign an approved consent form that conforms to federal and institutional guidelines.

